tofacitinib after in use in patients factors other than CV or malignan	ncy risk factors.
developing ≥1 VTE with VTE risk	
risk factors other than factors	
CV or malignancy risk	
factors while taking	
tofacitinib	
Continuation of Outcome: changes Defined as ≥1 VTE risk factor(s) v	while receiving tofacitinib
tofacitinib after in use in patients therapy (as listed and defined above	
developing ≥1 VTE with VTE risk dispensing for tofacitinib within a	
risk factors while factors the code for the first VTE risk fact	
taking tofacitinib	
Continuation of Outcome: changes The same definition as above but of	only limited to VTE risk
tofacitinib after in use in patients factors other than CV or malignan	
developing ≥1 VTE with VTE risk	1.01 1.01.1
risk factors other than factors	
CV or malignancy risk	
factors while taking	
tofacitinib	
Adherence to recommendations for limitations of use in patients aged 65 years and older (will be	
stratified by VTE reporting period 1, 2, 3 and CV and malignancy report period 1, 2, 3)	
Initiating tofacitinib Outcome: changes Defined as patients who are 65 years	
with no prior use of an in use in patients the index tofacitinib dispensing with no prior use of an in use in patients	
alternative therapy aged 65 years and dispensing for an alternative thera	
(i.e., biologic) among older months prior.	
patients 65 years of Complete list of biologics in ANN	NEX 7. LIST OF ATC
age and older CODES FOR MEDICATIONS O	
WHILE TAKING TOFACITINIE	
Discontinuation of Outcome: changes Defined as patients aged <65 year	
tofacitinib for patients in use in patients tofacitinib and discontinue tofaciti	
who turn 65 years old aged 65 years and old.	2
while receiving older	
tofacitinib Note: Patients may not discontinu	e tofacitinib immediately
after turning 65 years and need tin	
healthcare providers. Specific algo	
during SAP.	•
Continuation of Outcome: changes Defined as patients aged <65 year	s when initiating
tofacitinib for patients in use in patients tofacitinib, who have ≥1 prescription	
who turn 65 years old aged 65 years and tofacitinib within a specific time v	
while receiving older years and 0 prescription dispensin	
tofacitinib with no (i.e., biologic) prior to index tofac	
prior use of alternative dispensing.	
therapies Complete list of biologics in ANN	NEX 7. LIST OF ATC
CODES FOR MEDICATIONS O	
WHILE TAKING TOFACITINIB	

Table 3. Operational definitions of study variables in Système National des Données de Santé

Variable	Role	Operational definition
Continuation of	Outcome: changes	Defined as patients aged <65 years when initiating
tofacitinib for patients	in use in patients	tofacitinib, who have ≥1 prescription dispensing of
who turn 65 years old	aged 65 years and	tofacitinib within a specific time window after turning 65
while receiving	older	years and ≥1 prescription dispensing for an alternative
tofacitinib with prior		therapy (i.e., biologic) prior to index tofacitinib prescription
use of alternative		dispensing.
therapies		
	endations for limitation	ons of use in patients with CV risk factors (will be stratified
		, and CV and malignancy report period 1, 2, 3)
Assessment of CV risk for	actors prior to initiation	n of tofacitinib
History of	Outcome: changes	Defined as ≥1 ICD-10 diagnosis code for hyperlipidaemia or
hyperlipidaemia	in use in patients	≥1 prescription dispensing (as identified by ATC code[s]) for
	with CV risk	a statin or other antihyperlipidaemic in the 12 months prior
	factors	to the index tofacitinib dispensing.
		Complete list in ANNEX 9. LIST OF ATC CODES FOR
		ANTIHYPERLIPIDAEMICS.
Age ≥65 years	Outcome: changes	Defined as age at tofacitinib initiation ≥65 years
	in use in patients	
	with CV risk	
	factors	
History of coronary	Outcome: changes	Defined as ≥1 ICD-10 diagnosis code for MI or stroke or ≥1
artery disease (defined	in use in patients	procedure code for CABG or PCI in the 12 months prior to
as MI, stroke,	with CV risk	the index tofacitinib dispensing.
coronary artery bypass	factors	
graft [CABG] or		
percutaneous coronary		
intervention [PCI])		
History of stable	Outcome: changes	Defined as ≥1 ICD-10 code for stable angina pectoris in the
angina pectoris	in use in patients	12 months prior to the index tofacitinib dispensing.
	with CV risk	
	factors	
Current or past	Outcome: changes	Defined as ≥1 ICD-10 diagnosis code for tobacco use
smoker ¹	in use in patients	disorder or ≥1 procedure code for counselling visits for
	with CV risk	smoking or ≥1 prescription dispensing (as identified by ATC
	factors	code[s]) for a nicotine replacement product in the 12 months
		prior to the index tofacitinib dispensing.
History of diabetes	Outcome: changes	Defined as ≥1 ICD-10 diagnosis code for diabetes or at least
	in use in patients	3 reimbursements (or at least 2 in case of large pack sizes) of
	with CV risk	oral antidiabetic agents and/or insulin in the 12 months prior
	factors	to the index tofacitinib dispensing.
History of	Outcome: changes	Defined as ≥1 ICD-10 diagnosis code for hypertension or ≥1
hypertension	in use in patients	prescription dispensing (as identified by ATC code[s]) for an
	with CV risk	antihypertensive in the 12 months prior to the index
	factors	tofacitinib dispensing. Complete list in ANNEX 8. LIST OF
		ATC CODES FOR ANTIHYPERTENSIVES.

¹ Potential for very low sensitivity leading to misclassification. This variable will be reported if feasible

Table 3. Operational definitions of study variables in Système National des Données de Santé

Variable	Role	Operational definition
History of chronic kidney disease	Outcome: changes in use in patients with CV risk factors	Defined as ≥1 ICD-10 diagnosis code for chronic kidney disease in the 12 months prior to the index tofacitinib dispensing.
CV risk factor scores	Outcome: changes in use in patients with CV risk factors	Calculated as the sum of the number of CV risk factors (as listed and defined above) identified in the 12 months prior to the index tofacitinib dispensing. Weighting of CV risk factors may be considered as a sensitivity analysis to reflect the potential different importance of each risk factor.
Initiating tofacitinib with ≥1 CV risk factor (s)	Outcome: changes in use in patients with CV risk factors	Defined as ≥1 CV risk factor(s) (as listed and defined above) identified in the 12 months prior to the index tofacitinib dispensing (unless otherwise specified).
Initiating tofacitinib with ≥1 CV risk factor and no prior use of an alternative therapy (i.e., biologic)	Outcome: changes in use in patients with CV risk factors	Defined as ≥1 CV risk factor (as listed and defined above) identified in the 12 months prior to the day of the index tofacitinib dispensing and 0 prescription medication dispensing for an alternative therapy (i.e., biologic) in the 12 months prior to the date of the index tofacitinib prescription dispensing. Complete list of biologics in ANNEX 7. LIST OF ATC CODES FOR MEDICATIONS OF INTEREST TO AVOID WHILE TAKING TOFACITINIB.
Assessment of CV risk for versus < 65 years))	actors while receiving	tofacitinib therapy (will be stratified by sex and age (≥65 years
Hyperlipidaemia	Outcome: changes in use in patients with CV risk factors	Defined as ≥1 ICD-10 diagnosis code for hyperlipidaemia or ≥1 prescription dispensing (as identified by ATC code[s]) for a statin or other antihyperlipidaemic while receiving tofacitinib. Complete list in ANNEX 9. LIST OF ATC CODES FOR ANTIHYPERLIPIDAEMICS.
Age ≥65 years	Outcome: changes in use in patients with CV risk factors	Defined as age ≥65 years while receiving tofacitinib.
Current smoker	Outcome: changes in use in patients with CV risk factors	Defined as ≥1 ICD-10 diagnosis code for tobacco use disorder or ≥1 procedure code for counselling visits for smoking or ≥1 prescription dispensing (as identified by ATC code[s]) for a nicotine replacement product while receiving tofacitinib.
Coronary artery disease (defined as MI, stroke, CABG or PCI)	Outcome: changes in use in patients with CV risk factors	Defined as ≥1 ICD-10 diagnosis code for MI or stroke or ≥1 procedure code for CABG or PCI while receiving tofacitinib therapy.

Table 3. Operational definitions of study variables in Système National des Données de Santé

Variable	Role	Operational definition
Stable angina pectoris	Outcome: changes	Defined as ≥1 ICD-10 diagnosis code for stable angina
8 ₁	in use in patients	pectoris while receiving tofacitinib therapy.
	with CV risk	
	factors	
Diabetes	Outcome: changes	Defined as ≥1 ICD-10 diagnosis code for diabetes while
	in use in patients	receiving tofacitinib therapy.
	with CV risk	
	factors	
Hypertension	Outcome: changes	Defined as ≥1 ICD-10 diagnosis code for hypertension or ≥1
	in use in patients	prescription dispensing (as identified by ATC code[s]) for an
	with CV risk	antihypertensive while receiving tofacitinib.
	factors	Complete list in ANNEX 8. LIST OF ATC CODES FOR
		ANTIHYPERTENSIVES.
Chronic kidney	Outcome: changes	Defined as ≥1 ICD-10 diagnosis code for chronic kidney
disease	in use in patients	disease while receiving tofacitinib.
	with CV risk	
Discontinuation of	factors	Defined as >1 CV misk featon(a) while massiving tofesitinih
tofacitinib after	Outcome: changes	Defined as ≥1 CV risk factor(s) while receiving to facitinib therapy (as listed and defined above) plus 0 prescription
	in use in patients with CV risk	dispensing for tofacitinib within a specific time window after
developing ≥1 CV risk factors while taking	factors	the code for the first CV risk factor.
tofacitinib	Tactors	the code for the first C v fisk factor.
toracitinio		Note: The time window for when to look for a tofacitinib
		prescription dispensing will be specific to the CV risk
		factor(s) acquired while receiving to facitinib therapy and
		will be operationalised during SAP development.
		win so spermionansed during 2111 development.
		Duration of tofacitinib therapy defined in Section 9.3.2.
Continuation of	Outcome: changes	Defined as ≥1 CV risk factor(s) while receiving to facitinib
tofacitinib after	in use in patients	therapy (as listed and defined above) plus ≥1 prescription
developing ≥1 CV risk	with CV risk	dispensing for tofacitinib within a specific time window after
factors while taking	factors	the code for the first CV risk factor.
tofacitinib		
		ons of use in patients with malignancy risk factors (will be
		s), and CV and malignancy report period 1, 2, 3)
Assessment of malignan		
Age ≥65 years	Outcome: changes	Defined as age at tofacitinib initiation ≥65 years.
	in use in patients	
	with malignancy	
II: *** ** ** ** ** ** ** ** ** ** ** ** *	risk factors	Defined as \$1 ICD 10 House's and Consultaneous
History of malignancy	Outcome: changes	Defined as ≥1 ICD-10 diagnosis code for malignancy
(non-metastatic and	in use in patients	(excluding NMSC) in the 12 months prior to the index
metastatic, excluding	with malignancy risk factors	tofacitinib dispensing.
NMSC)	TISK Tactors	

Table 3. Operational definitions of study variables in Système National des Données de Santé

Variable	Role	Operational definition
Current or past smoker	Outcome: changes in use in patients with malignancy risk factors	Defined as ≥1 ICD-10 diagnosis code for tobacco use disorder or ≥1 procedure code for counselling visits for smoking or ≥1 prescription dispensing (as identified by ATC code[s]) for a nicotine replacement product in the 12 months prior to the index tofacitinib dispensing.
Malignancy risk factor scores	Outcome: changes in use in patients with malignancy risk factors	Calculated as the sum of the number of malignancy risk factors (as listed and defined above) identified in the 12 months prior to the index tofacitinib dispensing. Weighting of malignancy risk factors may be considered as a sensitivity analysis to reflect the potential different importance of each risk factor.
Initiating tofacitinib with ≥1 malignancy risk factor	Outcome: changes in use in patients with malignancy risk factors	Defined as ≥1 malignancy risk factor(s) (as listed and defined above) identified in the 12 months prior to the index tofacitinib dispensing.
Initiating tofacitinib with ≥1 malignancy risk factor and no prior use of an alternative therapy (i.e., biologic)	Outcome: changes in use in patients with malignancy risk factors	Defined as ≥1 malignancy risk factor (as listed and defined above) identified in the 12 months prior to the index tofacitinib dispensing and 0 prescription medication dispensing for a biologic (as identified by ATC code) in the 12 months prior to the index tofacitinib prescription dispensing. Complete list of biologics in ANNEX 7. LIST OF ATC CODES FOR MEDICATIONS OF INTEREST TO AVOID WHILE TAKING TOFACITINIB.
Assessment of malignan versus < 65 years))	cy risk factors while re	ceiving tofacitinib therapy (will be stratified by age (>65 years
Age ≥65 years	Outcome: changes in use in patients with malignancy risk factors	Defined as age ≥65 years while receiving to facitinib.
Malignancy (non- metastatic and metastatic, excluding NMSC)	Outcome: changes in use in patients with malignancy risk factor	Defined as ≥1 ICD-10 diagnosis code for malignancy (excluding NMSC) while receiving tofacitinib therapy.
Current smoker	Outcome: changes in use in patients with malignancy risk factor	Defined as ≥1 ICD-10 diagnosis code for tobacco use disorder or ≥1 procedure code for counselling visits for smoking or ≥1 prescription dispensing (as identified by ATC code[s]) for a nicotine replacement product while receiving tofacitinib.

Table 3. Operational definitions of study variables in Système National des Données de Santé

Variable	Role	Operational definition
Discontinuation of	Outcome: changes	Defined as ≥1 malignancy risk factor while receiving
tofacitinib after	in use in patients	tofacitinib therapy (as listed and defined above) plus
developing ≥1	with malignancy	0 prescription dispensing for tofacitinib within a specific
malignancy risk	risk factor	time window after the code for the first malignancy risk
factors while taking		factor.
tofacitinib		
		Note: The time window for when to look for a tofacitinib prescription dispensing will be specific to the malignancy risk factor acquired while receiving tofacitinib therapy and will be operationalised during SAP development.
Continuation of	Outcome: changes	Defined as ≥1 malignancy risk factor while receiving
tofacitinib after	in use in patients	tofacitinib therapy (as listed and defined above) plus
developing ≥1	with malignancy	≥1 prescription dispensing for tofacitinib within a specific
malignancy risk	risk factor	time window after the code for the first malignancy risk
factors while taking		factor.
tofacitinib		
Adherence to recomm	endations for limitation	ons of use in the JAKi referral (will be stratified by the
JAKi report period 1,		
A patient with CV or	Outcome: changes	Defined as an UC patient having ≥1 CV or malignancy risk
malignancy risk	in use of tofacitinib	factor(s) (as listed and defined above) from baseline to week
factors, an ADD of	following updated	16 and an ADD of >10 mg in any of the intervals: Weeks 17-
>10 mg in Weeks 17-	recommendations	24, Weeks 25-32, Weeks 33-40 and Weeks 41-48 of follow-
24, Weeks 25-32,	following the JAKi	up while receiving tofacitinib therapy.
Weeks 33-40 and/or	referral	
Weeks 41-48 of		This variable will be stratified by use of an alternative
follow-up and		therapy (i.e., biologic) in the 12 months prior.
evidence of a		
diagnosis for UC		
		ons of contraindicated use
Initiating tofacitinib	Outcome:	Defined as ≥1 ICD-10 diagnosis code for severe hepatic
with severe hepatic	Contraindicated	impairment in the 12 months prior to tofacitinib initiation.
impairment	use	
Initiating tofacitinib	Outcome:	Defined as tofacitinib initiation (i.e., the index date)
while pregnant	Contraindicated	occurring between the beginning and end of a pregnancy,
	use	using SNDS-specific algorithms developed.
		Complete list of pregnancy codes in ANNEX 11. LIST OF
		CODES FOR COMORBIDITIES
Receiving tofacitinib	Outcome:	Defined as evidence of a pregnancy while receiving
while pregnant	Contraindicated use	tofacitinib therapy using SNDS-specific algorithms.
Initiating tofacitinib	Outcome:	Defined as ≥1 ICD-10 diagnosis code for TB in the 60 days
while having TB	Contraindicated	prior to tofacitinib initiation.
(active or latent)	use	

Table 3. Operational definitions of study variables in Système National des Données de Santé

Variable	Role	Operational definition
Initiating tofacitinib	Outcome:	Defined as ≥1 ICD-10 diagnosis code for a serious and/or
while having a serious	Contraindicated	opportunistic infection in the 60 days prior to tofacitinib
and/or opportunistic	use	initiation.
infection		Complete list of serious and/or opportunistic infections in

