9.3. Variables

9.3.1. Variables and definitions

Table 3 summarises and defines the study variables to be collected and analysed in SNDS. Unless otherwise specified, these variables will be assessed during each patient's entire study period (baseline period and follow-up period).

This study will use code-based algorithms from the literature and/or other code lists to identify study variables. Published validated algorithms will be used where available.^{6, 7} All code-based algorithms and code lists will be reviewed and/or approved by Pfizer prior to

study initiation. Preliminary algorithms and/or codes are proposed in the following (Table 3); see also Annexes). Final algorithms and/or code lists may be refined as part of the statistical analysis plan (SAP) development. It is also to be noted that while laboratory tests performed are captured, results of laboratory tests are not available in the SNDS database.

Table 3. Operational definitions of study variables in Système National des Données de Santé

Variable	Role	Operational definition
Exposure		
Tofacitinib treatment	Exposure	Defined as having ≥1 ATC code (L04AA29) for a reimbursed prescription of tofacitinib during the indexing period. Index date is defined as the date of the first reimbursed prescription of tofacitinib.
Indication		
Indication	Indication (including off-label use)	Reported in the following categories: RA, PsA, UC and off-label/unknown based on hospital discharge diagnoses and active registration for diagnoses reported in the long-term disease (LTD) database for outpatients in the relevant time period. If there are no diagnosis codes for RA, PsA or UC, it will be categorised as off-label/unknown indications. Details will be further developed in the SAP.
		List of diagnoses codes for indications in ANNEX 13. LIST OF DIAGNOSIS CODES FOR INDICATIONS.
Primary Objective 1: I	Demographics, comorbi	dities and prior and current medications
		T OF CODES FOR COMORBIDITIES, unless otherwise
Age at tofacitinib initiation	Demographic	Calculated as the date of tofacitinib initiation minus the patient's month and year of birth and reported in the following categories: <18 years, 18-29 years and 30-39 years; 40-49 years; 50-59 years; 60-69 years; 70-79 years; ≥80 years; and <65 years and ≥65 years.
Sex	Demographic	Reported in the following categories: Male, Female and Unknown. Assessed on the date of the index tofacitinib prescription dispensing.

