9.4. Data sources

Data for this study will be obtained from SNDS database, which covers >99% (~ 65 million insures) of the French population from birth or immigration to death or emigration. The SNDS includes longitudinal claims data for inpatient and outpatient encounters by combining 3 main databases: the national hospital discharge database (PMSI), the health insurance claims database (Système National d'Informations Inter-Régimes de l'Assurance Maladie, SNIIRAM) and the national death registry. The PMSI was established in 2006 and captures information relating to inpatient or ambulatory care admissions to a public or private hospital in France. The SNIIRAM database captures data on socioeconomic characteristics and medical claims for medications, procedures and laboratory tests since 2003. The SNIIRAM database also includes the LTD registration data which captures information on the presence of LTD for which patients are eligible for 100% reimbursement of healthcare for the given disease. Data in the SNDS are updated bi-annually. Only variables relevant to this study, and available in the SNDS database, will be extracted.

As per the General Data Protection Regulation policy, only aggregated data with sample sizes >5 patients will be used for communications.

Details on the Health Insurance Data system, SNDS, are provided below in Table 4.

Table 4. Summary of Système National des Données de Santé database

Characteristics	SNDS
Database type	Claims
Country population	Over 65 million
Overall representativeness	Approximately 99% of the French population
Physician population	All
Expected number of tofacitinib	About 5,300 ^a
patients by the end of 2019	
Lag in data availability	12 months ^b

a Based on tofacitinib data from 2017-2019 that were obtained using the publicly available tools for querying the French national health registers

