9.7.2.1. Adherence to the recommended posology per indication and duration of use

Average daily dose, as listed in Table 3 and defined in Section 9.3.3, will be reported for each of the pre-specified time intervals as a continuous and categorical variable and may be stratified by presence of ≥ 1 major VTE risk factor(s) in the 12 months prior to tofacitinib initiation, pending sufficient sample size.

Duration of tofacitinib therapy, as listed in Table 3 and defined in Section 9.3.2, will also be described, tabulated and stratified by approved indication group ("RA or PsA" and "UC") and age (i.e., <65 and ≥65 years).

The variables listed under 'Outcome: Adherence to recommended posology' in Table 3 will be described and tabulated.

9.7.2.2. Adherence to patient screening and laboratory monitoring prior to and during tofacitinib treatment

The proportion of patients with evidence of having received the recommended screenings prior to initiation of tofacitinib and recommended monitoring after initiation of tofacitinib, as listed in Table 3, will be described and tabulated.

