9.9.2. Missing data and/or incomplete data

The French SNDS database and linked datasets are claims and hospital practice datasets where missing data are possible. Missing and/or incomplete data mainly applies to causes of death, which is not a variable of interest in this study. The use of multiple linked data sources (primary care, hospital, pharmacy data and central death registrations) has the potential to reduce missing and/or complete data and improve exposure and/or outcome ascertainment. Data on treatments administered over-the-counter or in hospital are not available (excluding for medications invoiced in addition to the hospital disease-related group) nor laboratory results, as described above.

To avoid missing or the input of inaccurate data, quality control processes are performed prior to the data being integrated in the SNDS.³¹

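### The protocol does not show that laboratory tests done during hospital stays are captured, so screening and monitoring adherence may be understated by an unknown amount.

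*Protocol*

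**What the plan says.** Section 9.3.1 of the protocol states that "while laboratory tests performed are captured, results of laboratory tests are not available in the SNDS database". The statement is not restricted to any care setting.

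Section 9.4 describes the database. At the top level, "The SNDS includes longitudinal claims data for inpatient and outpatient encounters by combining 3 main databases". Laboratory tests are named under one component only: "The SNIIRAM database captures data on socioeconomic characteristics and medical claims for medications, procedures and laboratory tests since 2003". The hospital component, PMSI, "captures information relating to inpatient or ambulatory care admissions to a public or private hospital in France"; tests are neither listed nor excluded there.

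Table 3 counts each screening or monitoring test as done on at least one procedure code or at least one ICD-10 code in the time window, and refers to Annex 10 for the laboratory codes. Annex 10 has a single code column, for biology codes.

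Section 9.7.2.2 reports "The proportion of patients with evidence of having received the recommended screenings prior to initiation of tofacitinib", and likewise for monitoring after initiation. There is no category for a patient whose test could not have been observed.

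On limitations, section 9.9.1.1 concedes that not all drugs given during hospital stays are fully captured. Section 9.9.2 says "Data on treatments administered over-the-counter or in hospital are not available", apart from separately invoiced medications. For laboratory data, sections 9.9.1.2 and 9.9.2 name missing results. Section 9.9.1.2 also says that the SAP will note any test that has no procedure code.

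**The concern.** Screening and monitoring adherence is part of Primary Objective 2. According to section 7, this study's data will help decide whether the risk minimisation materials work. The measure depends on the absence of a code meaning the absence of a test.

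The protocol asserts that tests are captured but does not support this for tests done during an inpatient or ambulatory hospital admission. It admits an in-hospital gap for drugs and argues that it hardly matters for tofacitinib exposure, because the drug is mostly reimbursed in outpatient settings. It makes no such argument for laboratory tests.

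If those tests leave no code, patients who were screened or monitored are reported as not tested, and prescribers look less adherent than they were. A wider confidence interval would not reveal this, because the error lies in classification and goes one way. The windows in Table 3 are 30 to 90 days long, so a single stay could hold a patient's only test in a window.

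**Working it through.** The protocol gives no figure that bears on this, so there is nothing to reproduce. The check sets the statements side by side and then illustrates the possible size.

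**What the text establishes**

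1. *Claim:* tests performed are captured (section 9.3.1), without limit.
2. *Named source of tests:* SNIIRAM claims (section 9.4). PMSI is described in general terms.
3. *Codes to be searched:* biology codes only (Annex 10). Table 3 also allows an ICD-10 code, but Annex 10 supplies none for any test. As written, that alternative has no codes behind it.
4. *Known in-hospital gaps:* medications (section 9.9.1.1) and treatments (section 9.9.2). The exception for medications invoiced on top of the hospital disease-related group shows that, for treatments at least, items inside the group payment are not visible.
5. *Tests during a stay:* no section says they are captured and none says they are missing.
6. *Consequence of no code:* the patient is in the denominator and not in the numerator (Table 3, section 9.7.2.2).

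Steps 5 and 6 together leave the direction of any error determined and its existence and size open.

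**Illustration**

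Let *t* be true adherence in a window, *h* the share of tested patients whose only test in that window was during a hospital stay, and *c* the share of those who are still found through a code. Then

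recorded adherence = *t* × (1 − *h* × (1 − *c*)).

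The protocol gives none of the three; all values below are assumptions. With *t* = 90%:

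| *h* | *c* = 0 (none captured) | *c* = 0.5 | *c* = 1 (all captured) |
|---|---|---|---|
| 5% | 85.5% | 87.75% | 90% |
| 10% | 81.0% | 85.5% | 90% |
| 20% | 72.0% | 81.0% | 90% |
| 30% | 63.0% | 76.5% | 90% |

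For example, 0.90 × (1 − 0.20 × 1) = 0.72, and 0.90 × (1 − 0.20 × 0.5) = 0.81. No entry exceeds 90%, because the bracket cannot exceed 1.

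**Check on the remedy**

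One candidate remedy is to drop only those patients who have a stay in the window and no code. Assume 100 patients, true adherence of 60% whether or not there is a stay, 30 patients with a stay, and every test captured.

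- With a stay: 30 × 0.60 = 18 tested, 12 not tested.
- Without a stay: 70 × 0.60 = 42 tested, 28 not tested.
- Planned proportion: (18 + 42)/100 = 60%, which is correct.
- Dropping the 12 with a stay and no code: 60/88 = 68.2%, which is too high.
- Dropping all 30 with a stay: 42/70 = 60%, which is correct here.
- Bounds on all patients: 60/100 = 60% if none of the 12 was tested, and 72/100 = 72% if all were.

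Dropping only patients without a code selects on the outcome and creates a bias where there was none. Dropping everyone with a stay, or giving bounds, does not.

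**The case against.** A reader might infer that the protocol, by its own description, shows in-hospital tests to be absent and adherence to be understated. The text does not go that far. Section 9.9.2 speaks of treatments, and for laboratory data it names only results. Section 9.4 says that the database covers inpatient as well as outpatient encounters, so arrival as a claim does not by itself mean outpatient only. The further step would need knowledge of how French hospitals bill laboratory work, which the protocol does not supply. This objection stands, and it limits the point to capture that has not been shown.

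It can also be said that Table 3 accepts an ICD-10 code, which gives a hospital route because such codes come from discharge and long-term disease records. The route exists on paper, but Annex 10 lists no ICD-10 code for any test. The lists are preliminary and may be refined, so the SAP could add some.

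A third argument is that laboratory codes are left to the SAP. What section 9.9.1.2 leaves to it is whether a procedure code exists for a test, and this can be settled without asking whether the code is complete across care settings. The point concerns an unqualified protocol statement and a bias direction missing from the limitations, not missing SAP detail.

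Finally, the share tested only in hospital is unknown, and section 9.9.1.1 says that tofacitinib is mostly reimbursed in outpatient settings. That is true. It concerns where the drug is reimbursed, not where the work-up was done, so it does not show the share to be small; nor does anything show it to be large.

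**Conclusion.** The point holds in limited form. The protocol states without qualification that laboratory tests performed are captured, but does not show this for tests done during hospital stays. If such tests leave no code, screening and monitoring adherence is understated, and the error cannot run the other way.

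Whether the loss exists, and how large it is, cannot be determined from the protocol. In the illustration above, recorded adherence ranges from 63% to 90% against an assumed true 90%; the range follows from the assumed inputs and is not an estimate. The documents do not support saying that adherence is understated, or that the error is concentrated in a particular group of patients.

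The change is worth making because the result belongs to a primary objective, the direction of any error is known, and the check is cheap. Section 9.9.1.1 already states the direction of bias for the proxy based on no prior alternative therapy. The laboratory measure deserves the same treatment if capture is incomplete.

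**What to change.** 1. Ask the database owner, whom section 9.9.1.2 already plans to consult on codes, whether tests done during inpatient and ambulatory hospital stays can be identified.
2. Keep the planned proportion in section 9.7.2.2 as the main figure.
3. In each test window, flag patients with a PMSI stay. Add one sensitivity analysis: either exclude every patient with a stay in that window, whether or not a code is found, or keep all patients and give bounds that count the flagged patients without a code as all tested and as none tested. Do not exclude only the flagged patients without a code.
4. If tests during stays cannot be identified, qualify the statements in sections 9.3.1 and 9.9.1.2 accordingly, and say in section 9.9 that adherence is biased downward. If they can be identified, say so there in one sentence.

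The cost is one flag from hospital stay dates, which come from a source that the study already uses, and extra table columns. The exclusion analysis has a smaller denominator and describes only patients without a stay in the window. The bounds keep everyone but may be wide if stays are common.
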